3.1.3 Follow-Up Phase

- Begins when the decision to discontinue a subject from treatment is made (no further treatment with study therapy).
- After completion of the first two follow-up visits, subjects will be followed every 3 months for survival.
- Follow-up assessments are to be collected as outlined in [Table 5.1-4](#).
- Subjects who discontinue treatment for reasons other than tumor progression will continue to have tumor assessments beginning 6 weeks (± 7 days) from the first dose of study drug for the first 12 months, and every 12 weeks (± 7 days) thereafter until documented tumor progression.
- Subjects will be followed for drug-related toxicities until these toxicities resolve, return to baseline or are deemed irreversible. All adverse events will be documented for a minimum of 100 days after last dose.

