8.3 Endpoint Definitions

8.3.1 Tumor Assessment Endpoints

8.3.1.1 Best Overall Response (BOR) per Subject

The best overall response is determined once all the data for the subject is known. It is defined as the best response designation, as determined by the investigator, recorded between the date of first dose of study drug and the date of objectively documented progression or the date of subsequent therapy, whichever occurs first. For subjects without documented progression or subsequent therapy, all available response designations will contribute to the BOR assessment.

In this study, BOR is specified for the intracranial, extracranial, and global compartments based on the (1) modified RECIST 1.1 criteria (intracranial), (2) RECIST 1.1 criteria (extracranial), (3) combination of modified RECIST 1.1 criteria and RECIST 1.1 criteria (global). Image assessment criteria (modified RECIST 1.1 and RECIST 1.1) are presented in [Appendix 3](#).

For the assessment of BOR, all available assessments per subject are considered.

The best overall response for each patient is determined from the sequence of overall (lesion) responses according to the following rules, listed in order of priority:

- CR = At least two determinations of CR at least 4 weeks apart before progression.
- PR = At least two determinations of PR or better at least 4 weeks apart before progression (and not qualifying for a CR).
- SD = At least one SD assessment \geq 6 months after start of treatment.
- PD = At least two determinations of PD at least 4 weeks apart after start of treatment (and not qualifying for CR, PR or SD).

The BOR for each patient will also be determined by the IRRC as specified within the CA209204 Imaging Review Charter.

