4 ENDPOINTS

4.1 Primary Endpoints

The primary endpoint is intracranial CBR. It is defined as the proportion of all treated subjects whose best overall response (BOR) is either a CR or PR or whose BOR was SD with duration of ≥ 6 months, as determined by modified RECIST 1.1 criteria for index intracranial lesions based on investigator review.

The BOR is defined as the best response designation recorded between the date of first study dosing date and the date of progression, or the date of subsequent anticancer therapy (including tumor-directed radiotherapy and tumor-directed surgery), whichever occurs first. In this study, BOR is specified for the intracranial, extracranial, and global compartments based on the (1) modified RECIST 1.1 criteria (intracranial), (2) RECIST 1.1 criteria (extracranial), (3) combination of modified RECIST 1.1 criteria and RECIST 1.1 criteria (global). Best response determination in trials where confirmation of complete or partial response is required: Complete or partial responses may be claimed only if the criteria for each are met at a subsequent time point as specified in protocol Appendix 3. There is no confirmation requirement for progressive disease (PD). The BOR for each patient as determined by the BICR is determined from a predefined set of rules specified within the Image Review Charter.

To ensure the accuracy of primary endpoints, analyses will be based on two sets of BOR: BOR as reported in the CRF and BOR with adjustment. BOR as reported in the CRF uses information entered in the CRF directly by investigators without adjustment. Results based on BOR with adjustments will serve as primary analysis. This decision was made after the interim database lock on 09 August 2020.

BOR with adjustment uses information entered in the CRF with the following adjustments:

- If BOR is NE, and the radiographic progression date is non-missing and prior to subsequent anti-cancer therapy start date, or subsequent anti-cancer therapy start date is missing, change BOR to PD.
- If BOR is SD, and the radiographic progression date is non-missing and duration of SD is less than 6 months and radiographic progression date is prior to subsequent anti-cancer therapy start date, or subsequent anti-cancer therapy start date is missing, change BOR to PD.
- If BOR is PR or CR, and there is preceding (confirmed or unconfirmed) PD and

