7.5.2.8 Progression Free Survival

The intracranial, extracranial and global PFS will be estimated using the Kaplan-Meier product-limit method, together with a two-sided 95% confidence interval for the median, calculated using the method of Brookmeyer and Crowley method.

PFS rates at 6, 12, 18, 24, 36, 48 months, and then every year will be estimated using KM estimates on the PFS curve. Minimum follow-up must be longer than the timepoint to generate the rate. Associated two-sided 95% CIs will be calculated. Results will be tabulated and plotted.

The source of progression event (death versus progression) will be summarized.

The status of subjects who are censored in the PFS KM analysis will be tabulated using the following categories:

- On-study (on-treatment, in follow-up)
- Off-study (lost to follow-up, withdrawn consent, never treated)
- Received subsequent anticancer therapy

All PFS data will be listed. In addition, a listing of subjects who were treated beyond progression will also be presented.

Sensitivity analyses using BICR-assessed PFS (intracranial, extracranial, and global) will also be performed for the above analyses and BICR PFS data will be listed.

In addition, to assess consistency of treatment effect in PFS in different subgroups, a ‘forest’ plot of the PFS rate at 6 month and two-sided 95% CIs based on Kaplan-Meier estimates will be produced on intracranial, extracranial and global PFS for the same variables as in section 7.5.2.2.

Primary censoring rules for the analysis of PFS are presented in Table 7.5.2.8-1.

Table 7.5.2.8-1: Censoring Scheme for Primary Definition of PFS

Situation	Date of Progression or Censoring	Outcome
No baseline tumor assessment	Date of first study treatment	Censored
No on-study tumor assessments and no death	Date of first study treatment	Censored
Documented progression	Date of first documented progression per RECIST 1.1 (excludes clinical progression)	Progressed
No progression and no death	Date of last evaluable tumor assessment	Censored
New anticancer therapy, tumor-directed radiotherapy, or tumor-directed surgery received without progression reported prior or on the same day	Date of last evaluable tumor assessment prior to initiation of subsequent therapy	Censored
Death without progression	Date of death	Progressed

[REDACTED]

In addition, a categorical summary of DOR will be presented for intracranial, extracranial and

[REDACTED]

[REDACTED]

[REDACTED]

[REDACTED]

[REDACTED]

[REDACTED]

[REDACTED]

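### The primary adjusted-BOR algorithm in SAP 4.1 enforces the cut at progression but not the cut at subsequent anticancer therapy that the same section defines

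*SAP*

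**What the plan says.** The primary endpoint in SAP 4.1 is the proportion of all treated subjects whose intracranial BOR "is either a CR or PR or whose BOR was SD with duration of ≥ 6 months", by investigator review.

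The same section limits BOR to what is "recorded between the date of first study dosing date and the date of progression, or the date of subsequent anticancer therapy", whichever is earlier, and it names tumor-directed radiotherapy and surgery as such therapy. Protocol 8.3.1.1 has the same two-way limit: "the date of objectively documented progression or the date of subsequent therapy, whichever occurs first".

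SAP 4.1 then describes two versions of BOR, one as entered on the CRF and one adjusted. The adjusted version is primary, a choice the SAP dates to after an interim database lock on 09 August 2020. For that version, "BOR with adjustment uses information entered in the CRF with the following adjustments". In summary, the adjustments are:

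- **NE** becomes PD if there is a radiographic progression date and it precedes subsequent therapy, or no subsequent therapy is recorded.
- **SD** becomes PD under the same date conditions, but only if SD lasted less than 6 months.
- **PR or CR** is reviewed on this trigger: "If BOR is PR or CR, and there is preceding (confirmed or unconfirmed) PD and". It becomes PD if progression came on or before the first response date. CR becomes PR if progression fell between the PR and CR dates.

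**The concern.** The definition closes the window at two events, but the algorithm that produces the primary result checks only one of them. The progression half has date-based rules for CR and PR. The therapy half has none, and SD of 6 months or more is never altered.

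Scans after a change of treatment are to be expected. Protocol 3.1.3 says: "Subjects who discontinue treatment for reasons other than tumor progression will continue to have tumor assessments". They run until progression, and starting another therapy is not named as a stopping point there or in Table 5.1-4. The PFS censoring table in SAP 7.5.2.8 has a row for new therapy given without prior progression, so the plan foresees such subjects.

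Take a hypothetical subject who stops study drug for toxicity at Week 6 with SD, starts another systemic anticancer drug at Week 10 without progression, and has PR at Weeks 18 and 24. If the site enters PR as the BOR, no adjustment applies and the subject counts as clinical benefit. Benefit that may belong to the later treatment is then credited to nivolumab plus ipilimumab in the CBR, and in ORR, which SAP 4.2 builds on BOR.

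**Working it through.** **Step 1. Compare each rule with the therapy cut.**

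- NE rule: its input is NE, so it cannot touch CR, PR or SD.
- SD rule: it requires SD under 6 months. Neither that SD nor the PD it becomes counts as benefit, so the therapy date used here cannot change CBR.
- PR/CR rules: they compare response dates with the progression date. No therapy date enters.

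The three categories that make up CBR therefore pass through unchanged when the only event before them is the start of subsequent therapy.

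**Step 2. Reproduce the plan's figures.** Inputs from SAP 5 and Protocol 8.1: n = 110, reference CBR 40%, alternative 51.8%, two-sided type I error 0.10. The exact 90% (Clopper-Pearson) lower bound for x successes is the 5th percentile of Beta(x, 110 − x + 1).

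- x = 53: 40.0%, as in both sample-size tables.
- x = 57: 43.6%, as in Protocol Table 8.1-1.
- Smallest x with P(X ≥ x | 110, 0.40) ≤ 0.05: x = 53, with tail probability 0.0499.
- Power, P(X ≥ 53 | 110, 0.518): 80.4%, as stated.

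**Step 3. Remove k subjects whose benefit came only after subsequent therapy.** The documents give no value for k, so 0 to 5 is an assumed range. Each subject is worth 1/110 = 0.9 percentage points, and five are worth 5/110 = 4.5 points.

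| Subjects with benefit | Observed CBR | Exact 90% lower bound |
|---|---|---|
| 57 | 51.8% | 43.6% |
| 56 | 50.9% | 42.7% |
| 55 | 50.0% | 41.8% |
| 54 | 49.1% | 40.9% |
| 53 | 48.2% | 40.0% |
| 52 | 47.3% | 39.1% |
| 51 | 46.4% | 38.2% |

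Starting at 53, one removal takes the bound below 40%. Starting at 57, four removals leave it at 40.0% and the fifth takes it to 39.1%.

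**Step 4. Effect on the error rate, under the same assumption.** If the true CBR is 40% and k/110 is wrongly added to it, the chance of reaching 53/110 is P(X ≥ 53 | 110, 0.40 + k/110):

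| k | 0 | 1 | 2 | 3 | 4 | 5 |
|---|---|---|---|---|---|---|
| Chance | 5.0% | 7.4% | 10.5% | 14.5% | 19.3% | 25.0% |

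**The case against.** The strongest reply is that the plan already excludes these responses. The definition stops at progression "or the date of subsequent anticancer therapy (including tumor-directed radiotherapy and tumor-directed surgery), whichever occurs first", the protocol agrees, and nothing says that the adjustments replace the definition. This stands in part. A response after a switch counts only if the investigator's entry departed from the definition, so a reader should not infer that the plan permits such responses. But the same definition also stops at progression, and the sponsor still wrote date-based rules for CR and PR entered after PD. Nothing in the documents makes the CRF entry more reliable for the therapy half.

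Other checks exist. Protocol 8.5.2 and SAP 7.5.1 plan a sensitivity analysis without on-study SRT patients and another with centrally assessed CBR, and SAP 7.5.2.2 cross-tabulates investigator and central BOR. The first does not cover drug switches or other local therapy. The second follows a charter that is not among the documents and is not primary. The tabulation of PFS censoring for subsequent therapy in SAP 7.5.2.8 would help bound the problem but would not correct the CBR.

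A reader might also infer a conflict with PFS, which censors such a subject at "Date of last evaluable tumor assessment prior to initiation of subsequent therapy". The definitions do not conflict, since both stop at subsequent therapy. Results would diverge only if a CRF entry broke the BOR definition.

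Nor can it be said that nothing anywhere ends SD duration at new therapy. The visible text does not define the start or end of that duration, parts of the SAP are redacted, and Protocol Appendix 3 is not available. What can be said is that no listed adjustment does so.

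On-study SRT is a weak route to the error. It is permitted for progression, so PD should usually come first, and the PR/CR rule would then act on a later response. What remains open is whether permitted SRT counts as tumor-directed radiotherapy for the window.

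**Conclusion.** The point holds as a gap between definition and algorithm. SAP 4.1 ends BOR at two events, and the adjustments behind the primary result do not enforce the second for CR, PR or SD of at least 6 months. Followed as written, the algorithm can return a CBR that breaks the SAP's own definition. For this error the direction is upward only.

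The size is unknown. It depends on how many subjects started other therapy before progression, had benefit recorded only afterwards, and had it entered as BOR. A reader might take the 53/110 figure to mean that the primary conclusion is fragile. That holds only at the boundary; at 57/110 the conclusion against 40% survives four such subjects. The documents do not show that any such subject exists, and the stated 80.4% power is correct.

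Severity is moderate. The cut is stated, so this is not a missing rule. It does concern the primary endpoint, and the adjusted version was made primary after an interim database lock, so its rules should be complete and checkable.

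**What to change.** Add a step to the adjusted-BOR list in SAP 4.1 for any subject whose subsequent anticancer therapy, as defined in that section, starts before progression:

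1. Re-derive BOR from assessments on or before the therapy start date. Any confirmation assessment the SAP requires for CR or PR must also fall on or before that date. Otherwise a PR first seen before the switch but confirmed only afterwards would still count.
2. End SD duration at the last evaluable assessment on or before that date, so that SD counts as benefit only if 6 months had been reached by then. State how SD duration is measured, or cite where it is defined.
3. State whether permitted on-study SRT counts as tumor-directed radiotherapy for this cut.
4. Report how many subjects the step changes, and from which category to which. They stay in the all-treated denominator.

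The cost is SAP wording and a small amount of programming with assessment and therapy dates the study already collects. The observed CBR may be slightly lower. If no subject changes, the report can say so, and the primary result will visibly match its definition.

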4.5.7 Treatment Beyond Initial Radiological Assessment of Disease Progression

As previously described in [Section 1.1.2.4](#), accumulating evidence indicates a minority of subjects treated with immunotherapy may derive clinical benefit despite initial evidence of PD.²³ This phenomenon was observed in approximately 10% of subjects in the Phase 1 study of nivolumab and has also been reported for ipilimumab monotherapy.

Subjects receiving treatment in this study will be permitted to continue treatment beyond initial PD (intracranial metastases using modified RECIST 1.1 criteria; extracranial disease by RECIST 1.1) as long as they meet the following criteria:

- Investigator assesses clinical benefit AND
- Subject is tolerating study drug.

If a patient has disease progression of ≤ 3 intracranial lesions, the patient may receive SRT (single episode) as clinically appropriate and then resume study treatment as outlined in [Section 3.4.2.2](#).

Subjects with confirmed progression (confirmation assessment will occur approximately 4 weeks after initially assessed progression) will be assessed radiographically and by clinical judgment as to whether the subject is deriving clinical benefit from treatment and should continue study treatment or discontinue and enter the follow up/survival phase of the study according to the time and events schedule presented in [Section 5](#). If progression is confirmed, then the date of disease progression will be the first date the subject met the criteria for progression.

All decisions to continue treatment beyond initial progression must be discussed with the BMS Medical Monitor and documented in the study records. Subject must provide written informed consent prior to receiving additional nivolumab treatment. All other elements of the main consent

including description of reasonably foreseeable risks or discomforts, or other alternative treatment options will still apply

For subjects who continue study therapy beyond progression, further progression is defined as an additional 10% increase in tumor burden volume from time of initial PD. This includes an increase in the sum of diameters of all target lesions and/or the diameters of new measurable lesions compared to the time of initial PD. Treatment with study medication should be discontinued permanently upon documentation of further progression.

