5.4.3 Confirmation of Scans

Verification of Response: Confirmation of intracranial response will be confirmed by an MRI performed approximately 4 weeks after the initial radiological assessment. If repeat scans confirm overall response (OR), then response should be declared using the date of the initial scan. If repeat scans do not confirm OR, then the subject is considered not to have had an OR.

Verification of Progression: Progression of disease should be verified in cases where progression is equivocal and will be confirmed by an MRI performed approximately 4 weeks after the initial radiological assessment of progression. If repeat scans confirm PD, then progression should be declared using the date of the initial scan. If repeat scans do not confirm PD, then the subject is considered not to have progressive disease.

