 - if the radiographic progression date is prior to or equal to the minimum of complete response date and partial response date, change BOR to PD;
 - if BOR is CR and both the complete response date and partial response date are non-missing and radiographic progression date is between those two, change BOR to PR.

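### SAP 4.1's primary adjusted BOR turns a response into PD after an earlier PD even when a repeat scan refuted that PD, which protocol 5.4.3 says is not progressive disease

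*SAP*

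**What the plan says.** **SAP 4.1** defines two versions of BOR, one as entered on the CRF and one with adjustments, and makes the adjusted version primary. It says this was decided after the interim database lock of 09 August 2020. The relevant adjustment has a trigger and two branches:

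- Trigger: "If BOR is PR or CR, and there is preceding (confirmed or unconfirmed) PD and"
- First branch: "if the radiographic progression date is prior to or equal to the minimum of complete response date and partial response date", in which case BOR becomes PD.
- Second branch: a CR with a PD dated between the PR and CR dates becomes PR.

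The same section says that PD needs no confirmation.

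**Protocol 5.4.3** says "Progression of disease should be verified in cases where progression is equivocal", by an MRI about 4 weeks later, and then: "If repeat scans do not confirm PD, then the subject is considered not to have progressive disease".

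**Protocol 4.5.7** says "Subjects receiving treatment in this study will be permitted to continue treatment beyond initial PD", under stated conditions. On dating, it says "If progression is confirmed, then the date of disease progression will be the first date the subject met the criteria for progression".

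**Protocol 8.3.1.1** defines a BOR of PD by at least two PD determinations 4 or more weeks apart, and only for subjects who do not qualify as CR, PR or SD.

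**SAP 7.5.1** also plans CBR from the CRF-reported BOR and a sensitivity analysis using blinded central review.

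**The concern.** Not requiring confirmation of a PD is different from overriding a repeat scan that was done and was negative. The SAP's trigger covers unconfirmed PD without separating a PD that was never rescanned from one that was rescanned and refuted. For the second kind the protocol gives a direct answer, and the SAP's primary analysis gives the opposite one.

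The sequence is foreseeable, because protocol 4.5.7 lets subjects stay on treatment after an initial PD and protocol 8.5.3 plans to estimate pseudoprogression. The study reports CBR as an estimate with a confidence interval, so a departure that works in one direction only can misstate the main result even though it is conservative. ORR is built on BOR, and SAP 7.5.2.2 analyses it in a similar way to intracranial CBR, so it inherits the same effect.

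**Working it through.** **1. One subject under both rules.** This is a hypothetical course on the protocol's schedule (scans every 6 weeks, verification at about 4 weeks): equivocal intracranial PD at week 6, repeat MRI at week 10 does not confirm it, PR at week 12, PR confirmed at week 16.

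- Protocol 5.4.3: the week 6 finding is not progressive disease. Protocol 8.3.1.1: there are not two PD determinations, and the subject qualifies for PR. BOR = PR, counted in CBR and ORR.
- SAP 4.1, if a radiographic progression date of week 6 is on the CRF: week 6 is before week 12, so BOR = PD, counted in neither.

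**2. Direction of each adjustment in SAP 4.1.**

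| Adjustment | Effect on CBR | Effect on ORR |
|---|---|---|
| NE to PD | none | none |
| SD under 6 months to PD | none | none |
| CR/PR to PD | minus 1 subject | minus 1 subject |
| CR to PR | none | none |

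The and/or wording of the SD rule is ambiguous. On a looser grouping, an SD of 6 months or more could also become PD, which again only lowers CBR. Enumerating combinations of BOR, SD duration and dates under both groupings gives no case in which CBR or ORR status rises.

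**3. The plan's own figures.** Inputs (protocol 8.1, SAP 5): n = 110, null rate 40%, alternative 51.8%, two-sided alpha 0.10.

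- Exact binomial: P(X ≥ 53 | 0.40) = 0.0499 and P(X ≥ 52 | 0.40) = 0.0730, so 53 is the critical count.
- P(X ≥ 53 | 0.518) = 0.804, matching the stated 80.4%.
- Clopper-Pearson 90% intervals: 53/110 gives 40.0% to 56.4% and 57/110 gives 43.6% to 60.0%, matching protocol Table 8.1-1.

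**4. Type I error.** The adjustments can only lower the count. If the true rate is 40%, the chance of reaching 53 therefore stays at or below 0.0499 in the upper tail.

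**5. Size per affected subject.**

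- Overall: 1/110 = 0.91 points.
- Cohort B at planned n: 1/20 = 5.0 points.

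**6. Illustration.** The starting count and the numbers affected are assumed; neither is in the documents as a result. The start is the design count of 57/110.

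| Assumed affected | Count | CBR | 90% lower limit |
|---|---|---|---|
| 0 | 57/110 | 51.8% | 43.6% |
| 4 | 57 − 4 = 53/110 | 48.2% | 40.0% |
| 5 | 57 − 5 = 52/110 | 47.3% | 39.1% |

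Five subjects (5/110 = 4.5%) would move the 90% lower limit below the 40% benchmark.

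**The case against.** The strongest reply is that the texts can be read together. The change to PD fires only if a radiographic progression date is recorded. Under protocol 5.4.3 a refuted PD is not a progression, and both 5.4.3 and 4.5.7 date progression back to the first scan only once it is confirmed. A site entering data on that basis would record no date, and the rule would not act. This stands as a reason why the number affected may be zero. It does not remove the conflict, because it rests on a CRF entry practice that neither document states.

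The direction is also conservative, and CRF-BOR and central-review analyses are planned. Both points are true and lower the stakes, but neither planned analysis is described as isolating refuted PDs.

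Protocol Appendix 3, which holds the response criteria, was not available to check.

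A reader might infer more than the documents support:

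- *That every unconfirmed PD conflicts with the protocol.* Section 5.4.3 asks for verification only of equivocal cases, the BOR window in 8.3.1.1 ends at objectively documented progression, and the protocol is not uniform on a single unrescanned PD. That case is outside the firm conflict.
- *That about 11 of 110 subjects is an upper bound.* Protocol 4.5.7 says "This phenomenon was observed in approximately 10% of subjects in the Phase 1 study of nivolumab", but that concerns benefit despite initial PD in another study. It neither counts nor bounds refuted PDs here.
- *That SAP 6.3's initial progression date shows refuted PDs carry dates.* That population also includes subjects with unequivocal or later confirmed PD.
- *That the CRF-BOR numerator minus the adjusted numerator counts the CR/PR-to-PD changes.* This holds only if the under-6-months condition of the SD rule applies to both branches of its or.
- *That no planned output gives the count.* The Data Presentation Plan is not supplied. The visible text does not specify such a count, and no more can be said.

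**Conclusion.** The point holds for one case: a PD refuted by a repeat scan, followed by a confirmed response, with a progression date left on the CRF. There the primary intracranial CBR and the ORR depart from protocol 5.4.3 and 8.3.1.1, downward only, by the per-subject amounts shown. It should be fixed, with moderate confidence: the textual conflict is clear, but its practical size is unknown and Appendix 3 is unseen.

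A reader might also infer a loss of power. The documents do not say which PD rule underlies the 51.8% design rate, so no power figure follows.

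**What to change.** **Check first** whether the CRF holds repeat-scan results and whether any refuted PD carries a progression date. The documents do not show this.

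**Preferred change.** In the SAP 4.1 trigger, replace the words covering confirmed or unconfirmed PD with: *preceding PD, other than one that a repeat scan under protocol 5.4.3 did not confirm*. Keep the current any-PD rule as a named sensitivity analysis. Report the number of CR/PR-to-PD changes that rest on a refuted PD, overall and by cohort.

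**Alternative**, if the sponsor prefers not to change the primary definition again after the interim lock: keep the current rule as primary, state that it departs from 5.4.3, and add the 5.4.3-consistent CBR and ORR as a sensitivity analysis with the same count.

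**Cost.** One clause of SAP wording, one programming change and one table. The main downside of the preferred change is that it comes after the lock, in an open-label, investigator-assessed study, and can only raise CBR relative to the present rule. It must be disclosed and justified by protocol 5.4.3.

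### SAP 4.1 resets a post-progression PR or CR straight to PD without checking for 6 months of SD before progression, so a narrow group loses clinical benefit in the primary endpoint

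*SAP*

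**What the plan says.** SAP 4.1 counts a treated subject as having intracranial clinical benefit if BOR is CR or PR, or if the subject is one "whose BOR was SD with duration of ≥ 6 months". On the window, it says "The BOR is defined as the best response designation recorded between the date of first study dosing date and the date of progression", with subsequent anticancer therapy closing it sooner if that comes first.

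Two sets of BOR are analysed: as entered on the CRF, and with programmed adjustments. Of the second, SAP 4.1 says "Results based on BOR with adjustments will serve as primary analysis".

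Two of the adjustments matter here:

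- **SD step.** An SD with a radiographic progression is changed to PD only if the SD lasted less than 6 months (and no subsequent therapy came before the progression).
- **PR/CR step.** The trigger is "If BOR is PR or CR, and there is preceding (confirmed or unconfirmed) PD and". The first sub-step applies if the radiographic progression date is "prior to or equal to the minimum of complete response date and partial response date, change BOR to PD". The second turns CR into PR when the progression date lies between the PR and CR dates.

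Protocol 8.3.1.1 ranks the categories. For partial response it has "PR = At least two determinations of PR or better at least 4 weeks apart before progression". SD needs an SD assessment at 6 months or later after the start of treatment. PD comes last and applies only to subjects who do not qualify for any of the other three.

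**The concern.** The PR/CR step is there to stop a response seen after progression from counting. That aim agrees with the BOR definition. But once the late response is discarded, the definition requires falling back to the best response before progression, and the first sub-step goes to PD in every case. The SD step protects 6 months of SD; this one does not.

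The records concerned can occur. Protocol 4.5.7 permits treatment beyond initial progression, and protocol 5.4 continues scans until progression or discontinuation of treatment, whichever is later.

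At stake is the classification of subjects in the primary endpoint. ORR is not affected by this gap, because SD and PD are both non-response.

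**Working it through.** **Six months in weeks.** SAP 8.1.2 sets 1 month = 30.4375 days. So 6 × 30.4375 = 182.6 days, and 182.6 / 7 = 26.1 weeks.

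**Constructed courses.** The sub-step compares the progression date with min(CR date, PR date). Scans are 6-weekly to Week 48 and 12-weekly after that; unscheduled MRIs are allowed.

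| Course | CRF BOR | Adjusted BOR under SAP 4.1 | Best response before progression |
|---|---|---|---|
| 1. SD Weeks 6 to 36, PD Week 42 (confirmed Week 46), PR Weeks 60 and 72 | PR | 42 ≤ 60, so PD: no benefit | SD of 6 months or more: benefit |
| 2. As course 1, no later response | SD | SD not under 6 months, so SD stays: benefit | SD of 6 months or more: benefit |
| 3. PR Weeks 12 and 18, PD Week 24, CR Weeks 30 and 36 | CR | 12 < 24 < 30, so PR: benefit | PR: benefit |

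In course 1 the first and last SD scans are 36 − 6 = 30 weeks apart, above 26.1, so the 6-month rule is met even on the strictest way of measuring duration. Courses 1 and 2 are identical up to and including progression, and only the subject who later responds is counted as a failure. Course 3 is a control in which the rule and the definition agree.

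**The date question.** Take PR at Week 12, PD at Week 16, PR at Weeks 24 and 30, CRF BOR of PR.

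- If the CRF partial response date is Week 12, then 16 ≤ 12 is false and PR stays, although only one PR determination precedes the PD.
- If it is Week 24, then 16 ≤ 24 is true and BOR becomes PD.

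The outcome turns on a date that the SAP does not define.

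**The plan's own figures.** The exact 90% lower bound L solves P(X ≥ x | n = 110, L) = 0.05.

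- 53/110 gives 40.0% to 56.4% and 57/110 gives 43.6% to 60.0%, as in protocol Table 8.1-1.
- Exact power at a true rate of 51.8%, rejecting at 53 or more, is 80.4%, as stated in SAP 5.

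**Size.** Each restored subject adds 1/110 = 0.91 points. The documents give no count, so the following are assumptions, starting from the planning value of 57/110:

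| Subjects restored | CBR | Exact 90% CI |
|---|---|---|
| 0 | 57/110 = 51.8% | 43.6% to 60.0% |
| 1 | 58/110 = 52.7% | 44.5% to 60.9% |
| 5 | 62/110 = 56.4% | 48.1% to 64.4% |
| 11 | 68/110 = 61.8% | 53.6% to 69.6% |

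The last row applies the roughly 10% that protocol 4.5.7 reports for benefit after initial progression in a Phase 1 study (0.10 × 110 = 11). I treat it as a generous ceiling, since subjects here must also have had 6 months of SD first.

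At the 40% reference the margin is one subject: the lower bound is 40.003% at 53/110 and 39.1% at 52/110.

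**The case against.** **The group is small.** To lose benefit, a subject must have 6 months of SD, progress, respond later, and have that late response entered as BOR although both documents close BOR at progression. This stands as a limit on scope. A reader might infer that anyone with long SD followed by progression loses benefit. That is wrong: with a CRF BOR of SD, the SD step keeps it (course 2). But a late response entered as BOR is exactly the record this step was written to handle, so it should handle it correctly.

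**Other analyses cover it.** SAP 7.5.1 also analyses CBR from unadjusted CRF BOR and from central review. In the CRF analysis these subjects count as benefit, so a gap between the two results would show. This stands in part. The gap would also contain subjects rightly reset to PD, and the CRF analysis credits a PR or CR that came after progression. Neither investigator-based set applies the stated definition.

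**An opposite, upward error.** A reader might infer that the step, including its CR-to-PR sub-step, also credits responses confirmed only after progression. The documents do not establish this. Protocol 5.4.3 treats a response that the repeat scan does not confirm as no response. An unconfirmed PR before progression should then drop out, the response date becomes the later one, and the step fires. A single PD followed by PR may also not be a real progression under protocol 5.4.3 or the two-determination PD rule of protocol 8.3.1.1. The upward error needs the CRF date field to hold an unconfirmed PR. The SAP is silent on that, and protocol Appendix 3, which it cites for confirmation, is not in the text available.

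**One subject at the boundary.** That arithmetic applies to any classification question at n = 110, and the planning value is four subjects above 53. This stands: it gives the scale and does not show that the conclusion would change.

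**Conclusion.** The point holds for the first sub-step of the PR/CR adjustment. It contradicts the BOR definition and the SD step in the same section, and the ranking in protocol 8.3.1.1. The contradiction follows from the text and needs no assumption about CRF dating.

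The effect on primary intracranial CBR is downward only, 0.91 points per affected subject. The number affected cannot be derived from the documents and may be zero. The stated sample size and power are not in question, and nothing here shows that the trial's conclusion would change.

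The undefined response dates are a second, conditional point. They warrant a clarification but do not support a claim of upward bias.

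This should be fixed: it is a wrong rule in the primary endpoint with a cheap remedy. By the SAP's own account, the adjusted set was chosen as primary after the interim database lock of August 2020, which is further reason for its rules to follow the stated definition exactly.

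**What to change.** 1. Reword the consequence in the first sub-step of SAP 4.1: *change BOR to SD if SD before the radiographic progression date, and before any subsequent anticancer therapy, meets the 6-month rule; otherwise change BOR to PD.* Measure the duration as the SD step does.
2. Define the dates: *the complete and partial response dates are initial-scan dates. A date before progression is used only if the confirming scan, at least 4 weeks later, also precedes progression. If there is no such date, the first sub-step applies.*
3. Because the change follows a database lock, date and document it, and report how many subjects it reclassifies, with CBR under both wordings.

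The cost is two sentences in the SAP and a small programming change. For the few subjects with a CRF BOR of PR or CR and a preceding PD, SD before progression must be read from the scan-level responses, since their CRF BOR entry does not show it. No new data are needed, and a full scan-level re-derivation of BOR for all subjects is not required.
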